#### 5) Insulin Sensitivity (Matsuda Index)

- a. Type of variable and level of measurement: Dependent, Quantitative of reason
- b. Indicator: natural numbers
- c. Conceptual definition: The ability of insulin to promote glucose uptake by muscle tissue, to suppress glucose production by the liver and to prevent lipolysis in adipose tissue.
- d. Operational definition: It will be evaluated using the Matsuda index with glucose and insulin values during the OGTT using the following formula:

$$\text{Insulin sensitivity} = \frac{10000}{\sqrt{(G_0 \times I_0) \times (G_{0-120} \times I_{0-120})}}$$

Where  $G_0$  = basal glucose

$I_0$  = basal insulin

$G_{0-120}$  = average glucose during OGTT

$I_{0-120}$  = average insulin during OGTT

This measurement will be carried out at the beginning and at the end of the intervention in each of the study groups.

## **6) Inflammation markers**

- a. Type of variable and level of measurement: Quantitative ratio
- b. Indicator: Corresponding measurement unit according to the biochemical marker
- c. Conceptual definition: Biochemical markers associated with a pro-inflammatory state
- d. Operational definition: Fasting serum levels of TNF $\alpha$ , IL6 and hsPCR
- e.

## **7) Cardiovascular function**

- a. Type of variable and level of measurement: continuous quantitative
- b. Indicator: %
- c. Conceptual definition: Comprehensive evaluation of the mechanical function of cardiac function, whose objective is to predict the risk of future cardiovascular events.
- d. Operational definition: It will be evaluated by the left ventricular ejection fraction, ventricular mass and diastolic and systolic preloads, by standard echocardiography performed by HRAEB Echocardiographic Cardiologist

## **GENERAL PROCEDURE**

### **Identification of patients**

The first phase will be carried out in collaboration with SSA First Contact Units, in the external consultation of Endocrinology, Diabetes, Obesity and Nutrition of the HRAEB and in the Metabolism Research Laboratory of the University of Guanajuato, León campus. During this initial phase, patients with obesity and at least 2 risk factors for DM2 will be identified, who will be invited to the study screening, as a first step they will answer a health survey that will include the evaluation of biological factors (physical activity, diet, drug addiction, risk factors for cardiometabolic diseases, etc.), psychological (quality of life, depression, behavior patterns, etc.) and social (family,

work environment, domestic violence, type of family, etc.). For this survey, questionnaires already validated and used in the Cohort study of Health Personnel being carried out at the Autonomous University of the State of Mexico and in the state of Morelos, by the Epidemiological Research Units and Health Services will be used from IMSS [109].

## **Patient Recruitment**

Evaluation and metabolic classification of patients: Both patients with a BMI > 30 Kg / m^2 and risk factors for DM2 will be invited to the HRAEB outpatient clinic and to the Metabolism Research Laboratory of the University of Guanajuato continue to the scrutiny phase and at this time they will be asked for the signature of informed consent; The next step will be to quote the patients in the Metabolism Research Laboratory of the University of Guanajuato, León Campus for fasting glucose measurement, and only patients who have a glucose level equal to or greater than 100mg / dL will be performed the OGTT to determine the presence of mixed prediabetes.

Oral Glucose Tolerance Test (OGTT): consists of citing the patient to the Metabolism Research Laboratory of the University of Guanajuato with an 8-12 h on fast, first cleaning will be performed from the site with antiseptic solution, the vein will then be channeled to the ulnar with a punzocat and the basal blood samples will be taken, then 75g of glucose will be given to drink and during the next two hours blood samples will be taken every 30 minutes (0, 30 , 60, 90 and 120min), administering after each blood sample 2cc of 0.9% saline, finally at the end of the study the catheter will be removed. During the OGTT, glucose will be determined and then insulin will be measured. As mentioned in the selection criteria, patients who are diagnosed with DM2 during screening (OGTT) will not be included in the study and will be informed of their diagnosis and will be advised to go to their treating physician to carry out their pharmacological treatment. .

According to glucose values at 2 h of the oral load, patients will be classified as:

1) Glucose normotolerant when glucose at 2h during OGTT is <140 mg/dl,

2) Patients with glucose intolerance when the glucose at 2h of the OGTT is between 140 and 199 mg/dl,

3) Patients with newly diagnosed DM2 when the glucose at 2 h of the OGTT is  $\geq$  200 mg/dl.

Only patients diagnosed with glucose intolerance in the OGTT will be invited to participate in the trial and those who accept will continue with a more thorough metabolic evaluation.

For this purpose, patients will have a complete medical history and the following studies:

- 1) Fasting baseline blood samples for measurement of: blood count, liver transaminases, lipid profile, inflammation markers (TNF alpha, IL-6, hsPCR, etc.) and insulin for the determination of HOMA-IR and HOMA- B.
- 2) Weight determination using a digital scale
- 3) Determination of body composition (% total fat, visceral fat,% total body water, bone mineral density, etc.) by DEXA analysis.

In this phase the screening of patients ends, and if at this time the patient agrees to continue in the intervention phase, the following will be done:

1) **Evaluation of cardiovascular function:** This will be done by standard echocardiography that will be performed in the Echocardiography area of the High Specialty Regional Hospital by a specialist in the area.

2) **Evaluation of renal function:** It will be carried out through 24-hour urine collection, in which creatinine clearance and 24-hour albuminuria will be measured.

3) **Randomization:** The patients will be randomized to one of the two interventions. It will be done by using a table of random numbers generated by a computer program. Patients will be randomized to receive, for 12 months, one of the following 2 interventions: 1) Quadruple therapy consisting of: 1 tablet every 24 h of linagliptin 2.5mg / metformin 850mg + 1 tablet every 24 h of empagliflozin 12.5mg / metformin 850mg + lifestyle modifications (personalized diet plan and individualized physical activity

indications), and 2) 1 tablet every 12 hours of Metformin 850mg + lifestyle modifications (personalized diet plan and individualized physical activity indications). The start of the dose in the two study groups will be gradual so that at one month of treatment the patient can be with full doses in each study group. In the quadruple therapy group it will be suggested to take the medication starting with half a tablet of linagliptin 5mg / metformin 850mg every 24 hours with the last meal of the day (dinner) and at 2-4 weeks increase the dose to 1 tablet every 24 hours; and another tablet containing empagliflozin 12.5mg / metformin 850mg starting with half a tablet every 24 hours, it will be indicated to take it with the first meal of the day (breakfast), and at 2-4 weeks complete the dose to 1 tablet every 24 hours; in the metformin therapy group it will be suggested to take the medication starting with half a tablet of metformin 850mg every 12 hours (in the morning with breakfast and half a tablet of metformin 850mg at night with dinner) and at 2 -4 weeks, complete the dose to 1 tablet every 12 hours.

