The mechanism of action of linagliptin is to inhibit the DPP-IV enzyme (dipeptidyl peptidase type IV); This enzyme (DPP-IV) has the biological effect of inactivating the glucagon-like peptide type 1 (GLP-1), so being inhibited by linagliptin this favors that the levels of endogenous GLP-1 rise up to 3.2 times by above the previous values (same that are reduced in patients with type 2 diabetes mellitus, which partly explains that these patients have a reduction in the incretin effect), which determines the biological effects of GLP-1 as stimulation of insulin secretion by pancreatic beta cells and inhibition of glucagon secretion by pancreatic alpha cells. This effect on the stimulation in insulin secretion is totally dependent on glucose levels, so it does not cause hypoglycemia. Linagliptin has a half-life of 12 h so it can be used every 12 or 24 h, it is eliminated by bile in more than 70% so it can be used in patients with kidney disease without dose adjustment, it offers a potential for achieve a sustained inhibition of more than 90% in DPP-IV for 24 h and is highly selective to inhibit DPP-IV compared to other enzymes such as DPP-8 and DPP-9, their doses range from 2.5 to 5mg / day . Linagliptin is indicated in the treatment of patients with uncontrolled type 2 diabetes mellitus, which does not cover control goals such as: glycosylated Hb less than 7%, fasting glucose less than 110mg / dl and postprandial glucose less than 140mg / dl. It can be used as a combination therapy with metformin, sulfonylureas, thiazolidinediones and insulins, either as double or triple therapies.

A randomized clinical trial was conducted in the Mexican population comparing the effect of linagliptin with metformin in subjects with glucose intolerance. Sixteen subjects with glucose intolerance, overweight or obesity were included. They were randomized into 2 groups, one group was treated with metformin and another with linagliptin, both for 3 months. The group that was treated with linagliptin obtained a significant decrease in glucose at 120 min. [110]

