### **Specific goals:**

1. Identify patients with glucose intolerance and obesity who may enter the study.
2. To assess the effect at 12 months with treatment with metformin 1700 mg / d and lifestyle modifications on insulin resistance, pancreatic islet function, and cardiovascular function in a group of patients with mixed prediabetes and obesity.
3. To assess the effect at 12 months of treatment with the combination of linagliptin 2.5 mg / metformin 850 mg every 24 h + Empagliflozin 12.5 mg / metformin 850 mg every 24 h and lifestyle changes on insulin resistance, the function of Pancreatic islet and cardiovascular function in a group of patients with mixed prediabetes and obesity.

4. Evaluate and compare cardiovascular risk markers (TNF $\alpha$ , IL6, hsPCR) before and after treatments in the 2 study groups.
5. Compare insulin resistance and pancreatic islet function between the study groups at the end of the intervention.
6. Evaluate and compare glucose metabolism using OGTT at the beginning and end of treatment in the study groups.

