### **MATERIAL AND METHODS**

**Type of study:** Single Center Parallel Clinical trial, randomized, double blind

**Study universe:** Mexican patients with mixed prediabetes and obesity.

**Study population:** Mexican patients with mixed prediabetes and obesity, from the State of Guanajuato.

**Location:** Regional High Specialty Hospital of Bajío and Division of Health Sciences of the University of Guanajuato, León, Gto.

**Type of sampling:** Non-probabilistic, of consecutive cases.

**Sample size:** The sample size calculation was performed based on the formula to compare proportions. We expect that quadruple therapy (linagliptin + empagliflozin + metformin + lifestyle modifications), improve at least 75% the outcome variables (insulin resistance, pancreatic islet function and cardiovascular function), at 6 months of initiated the intervention, as long as the standard therapy (metformin + lifestyle modifications) achieves only 30% [69-71, 73], so that the study is designed to detect a minimum difference of 45% between the study groups with a type I (alpha) error of 0.05 and a sample power of 80%, and according to the following formula [108]:

$$n = \frac{(Z_{\alpha/2} + Z_{\beta})^2 p_1(1-p_1)(r + 1)}{(d)^2 r}$$

Where,

$$(Z_{\alpha / 2} + Z_{\beta})^2 = 7.9$$

p1 = proportion of individuals in the best treatment who did not achieve improvement = 0.25

p2 = proportion of individuals in the worst treatment who did not achieve improvement = 0.70

r = ratio of individuals in the treatment groups = 1

d = difference expected to be found = 0.45

n = 14 + 20% of losses = 17 patients per group

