### Exclusion Criteria:

- Patients with diagnosed Type 2 Diabetes previously or detected during the OGTT
- Patients in actual treatment or during the last 3 months with metformin, pioglitazone or another antidiabetic drug, including insulin
- Serum creatinine > 1.6 mg/dL
- Hypertriglyceridemia very high (>500 mg/dL)
- Pregnant women
- Altered arterial hypertension (Systolic >180 mmHg or Diastolic >105 mmHg)
- Excessive alcohol intake, acute or chronic
- Medications or medical conditions that affect glucose homeostasis (thiazides, beta blockers, glucocorticoids for systemic use, weight-reducing drugs or anorexigenics, Cushing's syndrome, thyrotoxicosis)

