## **VARIABLES**

### **INDEPENDENT VARIABLE**

#### **1) Intervention**

a. Measurement level: Qualitative nominal

b. Indicator:

1. A for the group receiving quadruple therapy (linagliptin + empagliflozin + metformin + lifestyle modifications)
2. B for the group receiving standard therapy (metformin + lifestyle modifications)

c. Conceptual definition: Therapeutic strategy whose purpose is to avoid alterations in glucose metabolism and progression to DM2, and reduce cardiovascular risk.

d. Operational Definition:

1. When patients receive 1 tablet of linagliptin 2.5mg / metformin 850mg every 24 hours + 1 tablet of empagliflozin 12.5mg / metformin 850mg every 24 hours + lifestyle modifications for 12 months
2. When patients receive 1 tablet every 12 hours of metformin 850 mg + lifestyle modifications for 12 months

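### The dose-start instruction names a linagliptin 5 mg tablet, giving twice the 2.5 mg/day defined elsewhere; separately, the renal entry limit is looser than the protocol's own metformin contraindication

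*Combined protocol and SAP*

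**What the plan says.** **Linagliptin dose.** Three places agree on 2.5 mg/day:

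- Specific goals, item 3: "the combination of linagliptin 2.5 mg / metformin 850 mg every 24 h".
- Independent variable, 1) Intervention, operational definition: "1 tablet of linagliptin 2.5mg / metformin 850mg every 24 hours".
- Patient Recruitment, Randomization, where the two interventions are listed: "1 tablet every 24 h of linagliptin 2.5mg / metformin 850mg".

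Later in the same Randomization item, the text on gradual dosing has patients "starting with half a tablet of linagliptin 5mg / metformin 850mg every 24 hours with the last meal of the day (dinner"), followed by "at 2-4 weeks increase the dose to 1 tablet every 24 hours". It describes the end of this step-up, by one month, as the full dose.

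The background paragraph on linagliptin says of this drug that "their doses range from 2.5 to 5mg / day", and Table 1 lists it at 5 mg per 24 h.

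**Renal entry limit.** The exclusion criteria contain one renal rule: "Serum creatinine > 1.6 mg/dL". In the background, the metformin paragraph gives renal insufficiency as a contraindication, defined as creatinine above 1.5 mg/dL or 24-hour clearance below 30 ml/min. The empagliflozin contraindications use the same 30 ml/min clearance limit. Under Patient Recruitment, a 24-hour urine collection for clearance is listed as step 2 and randomization as step 3. Both come after the statement that screening has ended, and no threshold is attached to the result.

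**The concern.** The gradual-dosing text is the only place that gives the starting dose, the step-up and the meal timing, so it is what someone dispensing or instructing a patient would use. It contradicts the definition of the treatment under test. If it is followed, the experimental arm receives twice the linagliptin dose in the objectives, and the results are attributed to a dose that was not given.

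Nothing described in the plan would reliably expose the error. Adherence is checked by counting tablets at monthly visits, and one tablet a day counts the same at either strength. Nor is 5 mg obviously a misprint to a reader who has seen Table 1.

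The renal point concerns safety at entry. As written, the criteria admit a patient who meets the protocol's own stated contraindication to metformin, which both arms receive.

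**Working it through.** **Inputs.** Tablet strengths and frequencies are from the four places quoted above. The duration is 12 months, taken as 365 days. The step-up is at 2 to 4 weeks. Group size is from the sample-size paragraph: "n = 14 + 20% of losses = 17 patients per group".

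**Daily dose** = tablets per day × mg per tablet.

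| Step | 2.5 mg tablet (goals, definition, randomization list) | 5 mg tablet (dose-start instruction) | Ratio |
|---|---|---|---|
| Start, half a tablet | 0.5 × 2.5 = 1.25 mg/day | 0.5 × 5 = 2.5 mg/day | 2 |
| Full, one tablet | 1 × 2.5 = 2.5 mg/day | 1 × 5 = 5 mg/day | 2 |

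The defined full dose of 2.5 mg/day cannot be reached by following the dose-start instruction to its end. Half a tablet already supplies it, and the increase then overshoots it.

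**Cumulative exposure over 365 days** = starting days × starting dose + remaining days × full dose.

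- Step-up at 2 weeks (365 − 14 = 351 full-dose days): 14 × 1.25 + 351 × 2.5 = 895 mg as defined, against 14 × 2.5 + 351 × 5 = 1790 mg.
- Step-up at 4 weeks (365 − 28 = 337 full-dose days): 28 × 1.25 + 337 × 2.5 = 877.5 mg as defined, against 28 × 2.5 + 337 × 5 = 1755 mg.

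**The other components do not conflict.** Metformin in the quadruple arm is 425 + 425 = 850 mg/day at the start and 850 + 850 = 1700 mg/day at full dose. The standard arm, with two half tablets and then two whole tablets of 850 mg, gives the same figures. Empagliflozin is 12.5 mg per tablet in all four places. The discrepancy is confined to linagliptin.

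**Renal limits.** 1.6 − 1.5 = 0.1 mg/dL. A patient with creatinine above 1.5 and up to 1.6 mg/dL is eligible under the exclusion criteria but contraindicated for metformin under the background text. The clearance limit of 30 ml/min, given for both metformin and empagliflozin, has no counterpart in the exclusion criteria. The fasting bloods listed for screening do not name creatinine. The laboratory section mentions blood chemistry, so creatinine may well be measured, but no text ties a renal result to the decision to randomize.

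**The case against.** The strongest reply on dose is that this is a slip in one place. The operational definition and the list of interventions both say 2.5 mg, and the latter stands only a few lines before the 5 mg figure. Full dose most naturally means the dose just defined, and the Justification speaks of a low-dose combination. The strength a patient takes is that of the combination tablet the hospital supplies, so the dose is doubled only if a 5 mg tablet is actually dispensed, which nothing in the documents shows. Both doses lie within the stated range. The 17 patients include the 20% allowance for losses, so not all would complete a year.

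Much of this stands. It makes 2.5 mg the likely intent, makes the doubling conditional, and makes 17 patients for a full year an upper bound. It does not remove the contradiction. No text resolves it, and Table 1 makes 5 mg look plausible. Only the sponsor can confirm which strength was meant.

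On the renal point, the reply is that the background describes a drug while the exclusion criteria are the trial's rule, that the gap is small, and that the order of the steps implies clearance is known before allocation. Renal function is also measured again at 6 and 12 months, and patients are seen monthly. These are fair limits on the consequence. However, the later checks come after dosing begins, and a measurement without a threshold or a required review is not an eligibility rule.

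**Conclusion.** Both points hold, and the dose error is the one that matters. The dose-start instruction is wrong as written, by a factor of 2 at every step, assuming that the three concordant definitions state the intent. Worst case, if it is followed and a 5 mg tablet is supplied, up to 17 patients take 5 instead of 2.5 mg/day for 337 to 351 of 365 days, a total of 1755 to 1790 mg instead of 877.5 to 895 mg. This is a misstated experimental dose, not a dose outside the range the protocol gives. The sample size, the analysis and the metformin balance between arms are untouched. It should be fixed because it stands in a dosing instruction.

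The renal mismatch is real but small: 0.1 mg/dL on creatinine and a missing clearance limit. The documents give no creatinine distribution, so the number affected among about 34 patients (2 × 17) cannot be computed. I assume it is few.

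**What to change.** **Dose.** In the dose-start text of the Randomization item, change the linagliptin strength from 5 mg to 2.5 mg. The step-up then runs from 1.25 to 2.5 mg/day and agrees with the other three places. If the sponsor intends 5 mg, leave that text and amend specific goal 3, the operational definition and the list of interventions instead. The cost is one corrected figure, or three.

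**Renal.** In the exclusion criteria, set serum creatinine above 1.5 mg/dL and add 24-hour creatinine clearance below 30 ml/min. In the steps before randomization, require the clearance result to be reviewed before allocation. The urine collection is already planned, so the cost is waiting for its result and losing a few borderline patients.

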### **Intervention and follow-up**

All patients will receive nutritional guidance, meal plan and physical activation recommendations during the study at the Metabolism Research Laboratory of the University of Guanajuato and/or at the Metabolic Unit from the Hospital Regional de Alta Especialidad del Bajío. All patients will have a monthly follow-up with fasting glucose measurement, anthropometry, global clinical evaluation and adherence to treatment (by counting pills consumed monthly by the patient).

Adherence to drug treatment: Information about the disease, its possible complications, the purpose of the treatment to be followed, the exact dose, frequency of administration and duration of therapy, as well as the therapy will be transmitted in an adequate and understandable way to the patient. The consequences of not receiving it. The patient will be suggested to develop a plan as complex as possible and adapted to medications, doses and schedules with daily acts. Sort your medications by time sector (morning and night) and keep them in a visible place.

Nutritional treatment: a feeding plan will be given to each patient, with the aim of achieving a 7% weight loss during treatment. The total energy contribution must be adapted in order to maintain a recommended weight. The energy intake will be between 25 - 30 Kcal / kg/day. The recommended composition of the dietary regimen as follows: total fat 25 -30%, saturated fat <10%, with a predominance of monounsaturated (up to 15%); carbohydrates 50% -60 %; protein 15 – 20 % (1.2 g / body weight (kg) / day). Initially it is recommended to reduce the usual consumption 250 to 500 kcal / day. To determine the adherence to the dietary regimen , the food records of two days of the week and one day of the weekend, and the food consumption frequency questionnaire.

Physical activity: A minimum of 150 minutes per week of cardiovascular exercise and muscular endurance exercises (on non-consecutive days) will be recommended. In the case of sedentary patients, they should be recommended the practice of aerobic exercise, especially the walk, at least for periods of 20 to 30 minutes (periods of 10 continuous minutes are cumulative throughout the day), the application of The above indication should be done gradually, accompanied by the relevant instructions on precautions to avoid injury or other possible problems. In active patients they will be advised to increase time or intensity of physical activity. Physical activity will be assessed through the international physical activity questionnaire (IPAQ).

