intake of 450 kcal / day compared to approximately 250 kcal / day in the other two groups. The results showed that with intensive changes in lifestyle, the risk of DM2 was reduced by 58%, and with metformin by 31%; even so, the cumulative incidence of DM2 in 3 years was 14.4% in the intervention group, 21.7% in the metformin group, and 28.9 in the placebo group [71]. However, the long-term results (15 years) this intervention showed that the effect of the treatment is lost over time and that eventually the majority of patients will develop DM2.

In addition to metformin, other antidiabetic medications have been used: acarbose in a cohort of 1429 patients with ITG showed a reduction in DM2 risk of 25% with a necessary number to treat of 11 to avoid a case of DM2, however, more of the fourth part of patients did not complete the follow-up due to the side effects of the medication [72]; rosiglitazone in the DREAM study that included 5269 patients with GAA and / or ITG randomized to 4-8mg of rosiglitazone or placebo, at an average follow-up of 3 years, the rosiglitazone-treated group showed a DM2 risk reduction of 62% [73 ]; The ACT NOW study that used pioglitazone 45mg daily in subjects with GAA and / or ITG shows a risk reduction of DM2 of about 80% compared to placebo [74].

Currently, the pharmacological interventions used in patients with DM2, are directed towards pathophysiological alterations, that is, much emphasis has been made recently so that the treatment is implemented with a pathophysiology-based approach. In prediabetes, if we try to prevent the progression of the disease, it is clear that the options that may have a major impact on each of the pathophysiological alterations are those that could have the greatest effect to prevent the progression of the disease [26, 27, 43, 46, 75]; Within these pharmacological interventions, those that could be more effective, due to the pharmacological profile, are:

- **METFORMIN:** Metformin is the most widely used antidiabetic drug in the world. Although its main effect is exerted at the liver level, it also has an effect on other tissues such as muscle, adipose and pancreatic tissue, therefore its effects are related to the control of insulin resistance and / or pancreatic insulin secretion. At the liver level, metformin activates an enzyme known as AMP kinase (AMPK), which causes an

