### **DEPENDENT VARIABLES**

### **1) Improvement in glucose metabolism (regression of hyperglycemia and glucose intolerance)**

- a. Type of variable and level of measurement: Qualitative dichotomous nominal
- b. Indicator: Yes or No
- c. Conceptual definition: The ability of therapeutic interventions to reverse fasting hyperglycemia and glucose intolerance.
- d. Operational definition: It will be considered as YES when the fasting glucose level at 12 months after the start of the intervention is <100mg / dl and the glucose at 2h during the OGTT is <140mg / dl, and as NO when at 12 months after the start of the intervention, fasting glucose levels are  $\geq 100$ mg / dl and / or at 2h during OGTT are  $\geq 140$ mg / dl.

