### **Mid-term evaluation**

After 6 months of treatment, the patients of both study groups will be summoned to the Metabolism Research Laboratory of the University of Guanajuato León campus, with fasting from 8-12h for the completion of the OGTT, and the intermediate evaluation on the status of the glucose metabolism During this test blood samples will be taken at 0, 30, 60, 90 and 120 minutes to determine glucose and insulin, and obtain different rates of insulin resistance and insulin secretion. In addition, the evaluation of cardiovascular function and renal function will also be performed, using the methods previously mentioned. The hyperglycemic clamp will also be performed in the patients of both study groups.

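### Regression is scored from the 12-month glucose values alone, so a patient who develops diabetes, starts a non-study drug and normalises counts as a success of the assigned arm

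*Combined protocol and SAP*

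**What the plan says.** **At screening.** Patient Recruitment defines the finding by the 2-hour value, "Patients with newly diagnosed DM2 when the glucose at 2 h of the OGTT is" 200 mg/dl or more, and attaches a consequence: "patients who are diagnosed with DM2 during screening (OGTT) will not be included in the study and will be informed of their diagnosis", with advice to see the treating physician. The Exclusion Criteria match this, "Patients with diagnosed Type 2 Diabetes previously or detected during the OGTT", but apply at entry only.

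**After randomisation.** Intervention and follow-up says: "All patients will have a monthly follow-up with fasting glucose measurement, anthropometry, global clinical evaluation and adherence to treatment". At 6 months, Mid-term evaluation repeats the OGTT for "the intermediate evaluation on the status of the glucose metabolism", with glucose and insulin sampled every half hour up to 2 hours. Completion of the study repeats it at 12 months. None of these sections says what follows a diabetic-range value, and none mentions added glucose-lowering treatment.

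**The endpoint.** Dependent variable 1 sets two conditions. The first reads: "It will be considered as YES when the fasting glucose level at 12 months after the start of the intervention is <100mg / dl". The second is a 2-hour value below 140 mg/dl; anything else is NO. No condition refers to treatment received or to diabetes found earlier. The variable's conceptual definition concerns what the therapeutic interventions can reverse. The matching secondary objective is the percentage recovering normal tolerance in each group. Statistic Analysis gives chi-square for qualitative variables and has no rule for added treatment.

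**The concern.** The trial keeps measuring glucose in people at risk of diabetes, so it may well find some. The protocol body does not say what happens then. If a patient is given a non-study glucose-lowering drug, in or outside the trial, the endpoint cannot tell that patient from one who normalised on the assigned treatment. A failure of the assigned treatment would be counted as its success.

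The protocol already treats such drugs as a problem at entry, since it excludes anyone on an antidiabetic drug now or in the last 3 months. It has no counterpart after randomisation. The description of the intervention also names avoiding progression to diabetes as a purpose, yet no dependent variable records progression. A NO merges persisting prediabetes with new diabetes.

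**Working it through.** **Sections side by side**

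| Time | Measurement | Diabetes threshold given | Action stated in the protocol body |
|---|---|---|---|
| Screening | OGTT | 2-h ≥200 mg/dl | Not included, informed, advised to see physician |
| Monthly | Fasting glucose | None | None |
| 6 months | OGTT | As at screening (same test) | None |
| 12 months | OGTT | As at screening (same test) | None |

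Only the 6- and 12-month OGTTs repeat the screening finding. The monthly visits measure fasting glucose, for which the protocol gives a prediabetes range (100 to 125 mg/dl) but no diabetes threshold. The 12-month OGTT cannot itself produce the misscoring, because a diabetic-range value there is NO by definition. The scoring gap concerns patients who progress earlier.

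**Arm size (reproducing the plan).** From Sample size: 7.9 × 0.25 × 0.75 × 2 / 0.45² = 14.63, which the plan states as 14. Then 14 × 1.2 = 16.8, stated as 17 per group. I use 17 as the denominator; the figure is not disputed on this point.

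**How often progression might occur.** The input is the prevention trial cited in Treatment of Prediabetes: "the cumulative incidence of DM2 in 3 years was 14.4% in the intervention group, 21.7% in the metformin group". Assuming a constant hazard, annual risk = 1 − (1 − p)^(1/3).

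- Lifestyle: 1 − 0.856^(1/3) = 5.1% a year
- Metformin: 1 − 0.783^(1/3) = 7.8% a year

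For a 17-patient standard arm over 12 months:

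| Annual risk | Expected progressions (17 × risk) | Chance of at least one, 1 − (1 − risk)^17 |
|---|---|---|
| 5.1% | 0.9 | 59% |
| 7.8% | 1.3 | 75% |

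The quadruple arm would probably have fewer; the documents give no rate for it.

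**From progression to misscoring.** Two further steps are needed: a non-study drug is started, and by month 12 both fasting glucose is below 100 and 2-hour glucose below 140 mg/dl. The documents give no probability for either step. The number misscored is therefore unknown and smaller than the number progressing.

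**Weight of one patient.** 1/17 = 5.9 percentage points of an arm's regression rate, or 1/14 = 7.1 points if only the 14 patients left after the planned losses are analysed.

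**Direction.** A misscored patient raises the rate of his or her own arm. If progression and added treatment are commoner in the standard arm, that arm's rate rises and the observed advantage of quadruple therapy shrinks.

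**The case against.** **Silence is not an instruction.** A reader might infer that diabetes found by the trial would be left undisclosed for many months. The documents do not support that. No section tells staff to withhold a result, each month includes a clinical evaluation, and Ethical Considerations commits the trial to the Declaration of Helsinki and good clinical practice. The consent letter (Annex 1) was not available for this review and may cover disclosure. What stands is that the protocol body states no action.

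**The monthly visits do not repeat the screening finding.** This is correct: without a fasting threshold for diabetes, the inconsistency is confined to the later OGTTs. For the monthly visits there is a gap, not a contradiction.

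**The misscoring is hypothetical.** It needs three steps, and only the first can be gauged. A reader might take the chance of a progression as the chance of a misscored patient, or raise it by using the cited placebo rate (28.9% over 3 years) or the natural-history figure (25% over 3 to 5 years). Neither fits, since every patient here receives metformin and a lifestyle plan.

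**Counting observed values is a legitimate treatment-policy choice.** In general it is. Here, however, the conceptual definition asks what the trial interventions can reverse, and the plan never states that added treatment is to be ignored. Scoring such patients NO fits that concept better. The observed-value analysis belongs beside it.

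**The effect is limited.** A reader might infer that the gap flatters quadruple therapy. On the likelier pattern it does the opposite. It also touches a secondary objective; the main goal concerns islet function, insulin resistance and cardiovascular function.

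**Conclusion.** The point holds in a limited form. As written, dependent variable 1 would credit the assigned arm with a normal result reached on a non-study drug after progression to diabetes, contrary to its own concept. The protocol body also leaves open what follows a diabetic-range OGTT after screening.

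About 0.9 to 1.3 progressions are expected in a 17-patient standard arm over 12 months, and an unknown smaller number would be misscored, at 5.9 points each. This assumes a constant hazard and that the cited rates carry over. They could be too low, because the protocol describes combined prediabetes with overweight as the group most likely to progress. They could be too high, because the standard arm combines metformin with lifestyle change. The direction of bias, against the quadruple arm, assumes that added treatment is commoner in the standard arm, which is plausible but not shown.

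The change should be made: it is cheap, and with 17 patients per arm a single misscored case is visible in the result.

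**What to change.** 1. **Scoring.** Add to dependent variable 1: *a patient who starts any non-study glucose-lowering drug before the 12-month OGTT is classified as NO, whatever the 12-month values.* Report the observed 12-month classification as a sensitivity analysis.
2. **Recording.** Record progression to diabetes and its date, and the start date of any non-study glucose-lowering drug. Keep these patients in follow-up to month 12 and report progression by arm.
3. **Reconciliation.** Bring Patient Recruitment, Intervention and follow-up, Mid-term evaluation and Completion of the study into line on what follows a diabetic-range result after randomisation, including whether a fasting value counts as one. The content of that clinical rule is for the sponsor and the ethics committee.

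The cost is a few sentences and a few extra data fields; all glucose measurements are already scheduled. The downside is a slightly lower regression rate. The scoring rule covers only this endpoint and does not settle how added treatment is handled in the continuous outcomes.
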